2.2.2. Secondary Estimands

The secondary estimands for the secondary objective (immunogenicity) will use the hypothetical strategy and estimate the vaccine immune response when an intercurrent event does not occur. In other words, the immune response is estimated in the hypothetical setting where participants follow the study schedule and protocol requirements as directed. It includes the following 5 attributes:

 Population: Participants 18 through 64 years of age and ≥65 years of age, as defined by the inclusion and exclusion criteria.

Variables:

- HAI titers for each strain, by study intervention group with qIRV, at each time point.
- HAI titer fold rise for each strain, by study intervention group with qIRV, from before vaccination to each time point after vaccination.
- Presence of HAI seroconversion for each strain, by study intervention group with qIRV, at each time point after vaccination.
- Presence of HAI titers ≥1:40 for each strain, by study intervention group with qIRV, before vaccination and at each time point after vaccination.
- Presence of HAI seroconversion for all strains, by study intervention group with qIRV, at each time point after vaccination.
- Presence of HAI titers ≥1:40 for all strains, by study intervention group with qIRV, before vaccination and at each time point after vaccination.
- SARS-CoV-2—neutralizing titer for each strain, by study intervention group with a BNT162b2 dose.
- SARS-CoV-2-neutralizing titer fold rise for each strain, by study intervention group with a BNT162b2 dose, from before vaccination to each time point after vaccination.
- Presence of seroresponse for each strain-specific neutralizing titer, by study intervention group with a BNT162b2 dose.
- Treatment condition: μg qIRV/ μg bivalent BNT162b2 (original*/Omi BA.4/BA.5), μg qIRV μg bivalent BNT162b2 (original*/Omi BA.4/BA.5), μg qIRV μg bivalent BNT162b2 (original*/Omi BA.4/BA.5), μg qIRV, στ μg bivalent BNT162b2 (original*/Omi BA.4/BA.5) administered concurrently in the opposite arm to licensed QIV, administered on Day 1.

- Intercurrent events: The following intercurrent events could impact the interpretation or the measurement of the immune response:
 - Not receiving the vaccine as randomized.
 - Not meeting the study inclusion/exclusion criteria.
 - Having major protocol deviations (received prohibited vaccine or treatment that may alter the immune response and subsequently impact the vaccine protection).
 - Undergoing blood collection outside of the defined window (26 to 35 days, inclusive, after vaccination).

All data after intercurrent events, if collected, will be excluded.

- Population-level summary:
 - HAI GMTs at each time point and GMFRs from before vaccination to each time point after vaccination, and the proportion of participants achieving HAI seroconversion at each time point and the proportion of participants with HAI titers ≥1:40 before vaccination and at each time point after vaccination, will be estimated for each strain, by study intervention group with qIRV, for participants 18 through 64 years of age and ≥65 years of age separately.
 - SARS-CoV-2 GMT at each time point and GMFRs from before vaccination to each time point after vaccination, and the proportion of participants with seroresponse at 1, 4, and 8 weeks after vaccination, will be estimated for each strain by study intervention group with a BNT162b2 dose, for participants 18 through 64 years of age and ≥65 years of age separately.

*Original refers to the ancestral strain (Wuhan-Hu-1; USA-WA1/2020), also referred to in the protocol as the reference strain.

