- Perform 12-lead triplicate ECG. Any new ECG abnormality (compared to baseline) consistent with probable or possible myocarditis or pericarditis (as listed in Section 10.11.8.4.1) must result in further assessments as outlined in Section 10.11.8.8.10.
- Measure vital signs, including oral temperature, pulse rate, and seated blood pressure.
- Collect a blood sample of approximately 2.5 mL as detailed in the laboratory manual for troponin I laboratory testing as described in Section 8.3.4.
- Remind the participant to contact the site staff or investigator immediately if he or she
 experiences any of the following from Day 1 through Day 7 after vaccination
 (where Day 1 is the day of vaccination) to determine if an unscheduled reactogenicity
 visit is required:
 - Fever ≥39.0°C (≥102.1°F).
 - Redness or swelling at the injection site measuring greater than 10 cm (>20 measuring device units).
 - Severe pain at the injection site.
 - Any severe systemic event.
- Remind the participant to contact the site staff or investigator if a medically attended event (eg, doctor's visit, emergency room visit) or hospitalization occurs.
- Remind the participant to contact the site staff or investigator immediately if the
 participant experiences acute chest pain, shortness of breath, or palpitations
 (see Section 10.11.8.8.10).

- Schedule an appointment for the participant to return for the next study visit.
- Complete the source documents.
- The investigator or an authorized designee completes the CRFs.

10.11.8.8.4. Visit 3 – 1-Week Follow-Up Visit (After Vaccination) – 6 to 8 Days After Visit 1 for Substudy A

- Record AEs as described in Section 8.4.1.
- Record nonstudy vaccinations as described in Section 10.11.6.7.
- Record prohibited medication use as described in Section 10.11.6.7.1.
- Verify understanding of and compliance with protocol requirements for contraception as described in Section 5.3.1.
- Review laboratory results (troponin I) and ECG results. Any abnormal troponin I level
 must result in further assessments as outlined in Section 10.11.8.8.10.
- Perform 12-lead triplicate ECG. Any new ECG abnormality (compared to baseline) consistent with probable or possible myocarditis or pericarditis (as listed in Section 10.11.8.4.1) must result in further assessments as outlined in Section 10.11.8.8.10.
- Measure vital signs, including oral temperature, pulse rate, and seated blood pressure.

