4. ANALYSIS SETS (POPULATIONS FOR ANALYSIS)

Data for all participants will be assessed to determine if participants meet the criteria for inclusion in each analysis population prior to unblinding and releasing the database, and classifications will be documented per standard operating procedures.

Population	Description
Screened	All participants who sign the ICD.
Randomized	All participants who are assigned a randomization number in
	the IWR system.
Evaluable immunogenicity	All participants who are eligible, receive the study
	intervention to which they were randomized, have blood
	drawn for assay testing within the specified time frame
	(26-35 days after vaccination), have at least 1 valid and
	determinate assay result at the 4-week postvaccination visit,
	and have no major protocol violations.

Population	Description
mITT	All randomized participants who receive the study
	intervention and have at least 1 valid and determinate assay
	result after vaccination.
Safety	All participants who receive the study intervention.

Major protocol deviations will be determined by clinical review. A major protocol deviation is a protocol deviation that, in the opinion of the sponsor's study medical monitor, would materially affect assessment of immunogenicity or efficacy, eg, participant receipt of a prohibited vaccine or medication/treatment that might affect immune response or a medication error with suspected decrease in potency of the vaccine. The sponsor's medical monitor will identify those participants with protocol deviations before any analysis is carried out.

The APE field will be included in the PIPD form from the CORD system and is used to help identify protocol deviations that may exclude participants from a particular population. For each reporting event, the most current endorsed version of the PIPD list must be used to generate the protocol deviation data set for analysis and reporting.

The APE flags for this study are as follows:

YES-POP1 (participants excluded from the safety population)
YES-POP2 (participants excluded from the evaluable immunogenicity population)
YES-POP4 (participants identified as having multiple enrollments at different sites)

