6.2. Secondary Endpoints

6.2.1. Immunogenicity Endpoints

6.2.1.1. Main Analysis

- Estimand strategy: Hypothetical approach (Section 2.2.2).
- Analysis set: Evaluable immunogenicity population (Section 4).
- Analysis methodology: Descriptive summary statistics (Section 5.2.2).
- Analysis timing: 1, 4, and 8 Weeks after study intervention administration.
- Intercurrent events and missing data: All data collected after or at intercurrent events will be excluded. Antibody titers below the LLOQ will be treated as specified in Section 5.3.2. Missing data will not be imputed.
- Reporting results:
 - The SARS-CoV-2 GMT at each time point and GMFRs from before vaccination to
 each time point after vaccination, and the proportion of participants with seroresponse
 at 1, 4, and 8 weeks after vaccination, will be estimated for each strain, by study
 intervention group with a BNT162b2 dose, and separately by age group.
 - Descriptive statistics, including the sample size (n), GMTs, GMFRs, and 95% CI for the GMTs and GMFRs, will be presented for each strain by study intervention group with qIRV (Section 5.2.2), for participants 18 through 64 years of age and ≥65 years of age separately.
 - The proportion of participants achieving HAI seroconversion and the associated 2-sided Clopper-Pearson 95% CIs will be provided for each strain by study intervention group with qIRV, for participants 18 through 64 years of age and ≥65 years of age separately.
 - o The proportion of participants with HAI titers ≥1:40 before vaccination and at each time point after vaccination and the associated 2-sided Clopper-Pearson 95% CIs will be provided for each strain by study intervention group with qIRV, for participants 18 through 64 years of age and ≥65 years of age separately.
 - HAI GMTs for each strain and the associated 95% CIs will be plotted by study intervention group with qIRV, for participants 18 through 64 years of age and ≥65 years of age separately.
 - HAI seroconversion rate for each strain, along with the associated 95% CIs, will be presented by study intervention group with qIRV, for participants 18 through 64 years of age and ≥65 years of age separately.

- SARS-CoV-2 GMT at each time point and GMFRs from before vaccination to each time point after vaccination, and the proportion of participants with seroresponse at 1, 4, and 8 weeks after vaccination, will be provided for each strain by study intervention group with a BNT162b2 dose, and separately by age group.

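### Substudy A SAP: the 26–35 day blood-draw window is not tied to the 4-week visit, so the exclusion rule as written contradicts the planned week-1, week-4 and week-8 analyses

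*SAP*

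**What the plan says.** All SAP references are to the Substudy A plan (version 2, matched to protocol Amendment 2).

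- **The event.** Section 2.2.2 uses a hypothetical strategy for the secondary immunogenicity estimands. Its list of intercurrent events includes "Undergoing blood collection outside of the defined window (26 to 35 days, inclusive, after vaccination". No visit is named. Section 2.2.3 repeats the item for the exploratory variant-of-concern estimands.
- **The consequence.** Section 2.2.2 states: "All data after intercurrent events, if collected, will be excluded". Section 6.2.1.1 is wider: "All data collected after or at intercurrent events will be excluded". Section 6.3.1.1 likewise drops data at or after the event for the exploratory endpoints.
- **The planned results.** Section 6.2.1.1 sets "Analysis timing: 1, 4, and 8 Weeks after study intervention administration". The population-level summary in 2.2.2 includes "the proportion of participants with seroresponse at 1, 4, and 8 weeks after vaccination".
- **The schedule.** The protocol (10.11.1 and 10.11.8.8.4 to 10.11.8.8.6) places the week-1 draw at "6 to 8 Days After Visit 1 for Substudy A", the week-4 draw at 26 to 30 days and the week-8 draw at 52 to 60 days.
- **The analysis set.** Section 4 puts the same 26–35 day window in the evaluable immunogenicity definition, next to the requirement for a valid and "determinate assay result at the 4-week postvaccination visit".

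**The concern.** The estimand is meant to describe participants who keep to the schedule. As written, keeping to the schedule is what triggers the exclusion, because the week-1 and week-8 visits lie wholly outside the only window the rule gives.

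The consequence also does not suit this type of event. Excluding everything from the event onward makes sense for a prohibited vaccine, which can alter every later titer. A mistimed draw affects only the sample taken that day.

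At stake are the GMTs, GMFRs, seroconversion and seroresponse rates at weeks 1, 4 and 8. A programmer who follows the text cannot produce all of the outputs that the same SAP requires. One who does not follow it must decide, without guidance, which week-1 and week-8 samples count as in window.

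**Working it through.** The plan gives no figure to reproduce here. The check compares visit days with the window and then applies the exclusion wording.

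**Step 1. Scheduled days inside 26–35** (visit days from protocol 10.11.1, window from SAP 2.2.2)

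| Visit | Scheduled days | Days inside 26–35 |
|---|---|---|
| Week 1 | 6–8 | 0 of 3 |
| Week 4 | 26–30 | 5 of 5 |
| Week 8 | 52–60 | 0 of 9 |

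Every on-schedule week-1 and week-8 draw is therefore an intercurrent event on the text of 2.2.2. Every on-schedule week-4 draw is not.

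**Step 2. Apply the exclusion to a fully compliant participant**, with draws on days 7, 28 and 56. The prevaccination sample is left aside, since the window counts days after vaccination.

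The first event is the day-7 draw.

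- *At or after the event* (6.2.1.1): day 7 is excluded as the event itself; days 28 and 56 are excluded because they follow it. Draws kept: none.
- *After the event* (2.2.2): day 7 stays; days 28 and 56 are excluded. Draws kept: week 1 only.

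The two sections thus give different answers for the same participant. Neither leaves the week-4 result, which is the time point the evaluable set is built on.

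**Step 3. Apply the rule with the window limited to week 4, and weeks 1 and 8 given 6–8 and 52–60 days.** Days 7, 28 and 56 are each inside their own window. No event occurs and all three draws are kept.

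**Step 4. Look for another rule that settles the matter.** Section 6.5.2.2 tabulates, for each sampling time point, how many samples fall within, before and after the protocol time frame, but it attaches no exclusion. The protocol visit window cannot simply be assumed to be the analysis window: at week 4 the SAP uses 26–35 days where the protocol visit is 26–30. So the SAP has no stated rule for an out-of-window week-1 or week-8 sample.

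**The case against.** The strongest reply is that nobody would apply the rule this way. Section 2.2.2 defines its hypothetical setting by adherence to the study schedule, and a draw on days 6–8 or 52–60 is the schedule. Section 4 places the same window beside the 4-week result, and the SAP orders reporting at weeks 1 and 8. Read together, 26–35 days is the week-4 window with its label left off. A literal reading that empties the immunogenicity analysis is itself evidence that it was not intended. This stands as to intent. It does not change what the operative rule says, nor supply the missing rule for weeks 1 and 8.

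The consequence is also limited. Substudy A is descriptive and its primary objective is safety. Amendment 6 moves weeks 1 and 8 to exploratory in its objectives, although this SAP still holds them as secondary. That stands too, but the results are still planned under either label.

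Three stronger readings might be inferred, and the documents do not support them:

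- *That the trial will discard these samples.* The context points to the week-4 reading, so data loss is not the expected outcome.
- *That exactly the week-1 and week-8 draws, two of every three, are lost.* This needs each out-of-window sample to be dropped on its own. Neither section says so: one wording removes all three draws, the other removes weeks 4 and 8.
- *That evaluability should be decided visit by visit, so that a participant without a valid week-4 result keeps weeks 1 and 8.* The 4-week requirement is the protocol's own definition (10.11.9.2). A single evaluable set is a defensible trade-off, and a supplementary mITT analysis is available as an option.

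**Conclusion.** The point holds as a drafting error in an operative rule. Sections 2.2.2 and 2.2.3 make any draw outside 26–35 days an intercurrent event, and the exclusions attached to it contradict the week-1, week-4 and week-8 results that the SAP commits to. For a participant who attends week 1 on schedule, the text removes all three postvaccination draws (6.2.1.1) or two of the three (2.2.2).

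That is the size of the contradiction, not an estimate of what will happen. It rests on taking the words as they stand, on the protocol's visit windows, and on the postvaccination draws alone. On the likely intended reading the week-4 results are unaffected. What remains is that the handling of out-of-window week-1 and week-8 samples is unspecified. Primary safety analyses are not touched.

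**What to change.** In Sections 2.2.2 and 2.2.3:

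1. Tie the 26–35 day window to the 4-week visit by name.
2. State analysis windows for weeks 1 and 8, for example the protocol's 6–8 and 52–60 days.
3. State that a draw outside its visit's window excludes that visit's sample only, and keep the at-or-after exclusion for events that can affect later titers. Align 2.2.2, 6.2.1.1 and 6.3.1.1 on one wording.

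Leave the evaluable-population definition unchanged. A participant without an in-window draw and a valid result at week 4 stays outside that set at every visit, as now.

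The cost is a wording change in the SAP and a visit-specific window check in the programming. No new data are needed, nor any change to the protocol's analysis sets. The change should be made before the immunogenicity analyses are programmed or, if that has been done, the rule actually applied should be documented.

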2.2.3. Additional Estimands

The additional estimands for the tertiary/exploratory objective will use the hypothetical strategy. It includes the following 5 attributes:

 Population: Participants 18 through 64 years of age and ≥65 years of age, as defined by the inclusion and exclusion criteria.

Variables:

 SARS-CoV-2 VOC-neutralizing titer for VOCs not already specified, by study intervention group with a BNT162b2 dose.

- SARS-CoV-2 VOC-neutralizing titer fold rise for VOCs not already specified, by study intervention group with a BNT162b2 dose, from before vaccination to each time point after vaccination.
- Presence of seroresponse for VOCs not already specified, by study intervention group with a BNT162b2 dose.
- Treatment condition: Leg µg qIRV/Leg µg bivalent BNT162b2 (original*/Omi BA.4/BA.5), Leg µg qIRV/Leg µg bivalent BNT162b2 (original*/Omi BA.4/BA.5), Leg µg qIRV/Leg µg bivalent BNT162b2 (original*/Omi BA.4/BA.5), or Leg µg bivalent BNT162b2 (original/Omi BA.4/BA.5) administered concurrently in the opposite arm to licensed QIV, administered on Day 1.
- Intercurrent events: The following intercurrent events could impact the interpretation or the measurement of the immune response:
 - Not receiving the vaccine as randomized.
 - Not meeting the study inclusion/exclusion criteria.
 - Having major protocol deviations (received prohibited vaccine or treatment that may alter the immune response and subsequently impact the vaccine protection).
 - Undergoing blood collection outside of the defined window (26 to 35 days, inclusive, after vaccination).

All data after the above intercurrent events, if collected, will be excluded.

 Population-level summary: GMTs and GMFRs of SARS-CoV-2 VOC-neutralizing titers for VOCs not already specified, and associated 2-sided 95% CIs, will be estimated by study intervention group with a BNT162b2 dose for participants 18 through 64 years of age and ≥65 years of age separately.

*Original refers to the ancestral strain (Wuhan-Hu-1; USA-WA1/2020), also referred to in the protocol as the reference strain.

2.3. Study Design

This is a Phase 1 randomized, open-label substudy to describe the safety and immunogenicity of up to 3 dose-level combinations of qIRV/bivalent BNT162b2 (original/Omi BA.4/BA.5). Approximately 360 participants will be enrolled across 2 age strata: approximately 180 participants 18 through 64 years of age and approximately 180 participants ≥65 years of age. The participants will be randomized equally (30 participants per group) to receive a dose of either:

 qIRV/bivalent BNT162b2 (original*/Omi BA.4/BA.5), at 1 of the 3 dose-level combinations shown in Table 2.

- μg qIRV,
- μg qIRV, or
- μg Bivalent BNT162b2 (original/Omi BA.4/BA.5) administered concurrently in the opposite arm to licensed QIV.

Table 2. Study Interventions and qIRV/Bivalent BNT162b2 (Original/Omi BA.4/BA.5) Dose-Level Combinations

Group Number	Dose-Level Combination	qIRV Dose	Bivalent BNT162b2 (Original/Omi BA.4/BA.5) Dose	Total modRNA Dose
1	1	CCI CCI	 μg, ie, μg of original BNT162b2 and μg of BNT162b2 Omicron (B.1.1.529 sublineage BA.4/BA.5) 	ССІ µg
2	2	ug, ie,	e μg, ie, μg of original BNT162b2 and μg of BNT162b2 Omicron (B.1.1.529 sublineage BA.4/BA.5)	μg
3	3	CCI ug, ie,	μg, ie, μg of original BNT162b2 and μg of BNT162b2 Omicron (B.1.1.529 sublineage BA.4/BA.5)	μg
4	N/A	ug, ie,	N/A	μg
5	N/A	CCI CCI	N/A	μg
6	N/A	N/A	(original/Omi BA.4/BA.5), administered concurrently in the opposite arm to licensed QIV	μg

As determined based on emergent data from ongoing clinical studies with BNT162b2, dose-level combinations 1 and/or 3 may be omitted from this study. Safety and immunogenicity data from studies previously conducted in participants of a similar age range having received 1 dose of BNT162b2 at a dose level of participants of a similar age as a control during analysis.

^{*}Original refers to the ancestral strain (Wuhan-Hu-1; USA-WA1/2020), also referred to in the protocol as the reference strain.

3. ENDPOINTS AND BASELINE VARIABLES: DEFINITIONS AND CONVENTIONS

3.1. Primary Endpoints

- Local reactions through 7 days following vaccination.
- Systemic events through 7 days following vaccination.
- AEs through 4 weeks after vaccination.
- SAEs through 6 months after vaccination.
- Abnormal troponin I laboratory values 2 days and 1 week after vaccination.
- New ECG abnormalities 2 days and 7 days after vaccination.

3.1.1. Local Reactions

The local reactions reported in the e-diary are redness, swelling, and pain at the injection site, from Day 1 through Day 7 after vaccination, where Day 1 is the day of vaccination. This section describes derivations with details for the assessment of local reactions: any presence, maximum severity, duration, and onset day of local reactions, in addition to the presence of severe local reactions on each day.

Presence or Absence

For the data summary of the presence (yes or no) of a local reaction during the interval from Day 1 through Day 7 after each vaccination, where Day 1 is the day of vaccination, the following variables are required to compute the proportions:

- Presence (yes or no) of each severe/Grade 4 local reaction on each day and any day (Day 1 through Day 7).
- Presence (yes or no) of each local reaction, by maximum severity, on any day (Day 1 through Day 7).

For each local reaction and any local reaction on any day, Table 3. explains the algorithm to derive the presence of a reaction (yes or no) during the interval from Day 1 through Day 7, where Day 1 is the day of vaccination.

Table 3. Derived Variables for Presence of Each Local Reaction Within 7 Days
After Vaccination

Variable ^a	Yes (1)	No (0)	Missing (.)
Presence of each	The reaction is reported	The reaction is reported as	Participant does not report
local reaction.	as "yes" with a diameter	"no" (or "yes" with a diameter	any data on all 7 days
	of >2.0 cm for	≤2.0 cm for redness/swelling)	(Day 1 through Day 7) for
	redness/swelling or "yes"		the reaction.
	for pain any day from	combination of "no" and	
	Day 1 through Day 7.	missing on all 7 days.	

a. The variables will be derived for each of the local reactions (redness, swelling, and pain at the injection site) and for each of the severe local reactions within the interval from Day 1 through Day 7 after vaccination.

Table 4. Derived Variables for Presence of Any Local Reaction Within 7 Days After Vaccination

Variable ^a	Yes (1)	No (0)	Missing (.)
Presence of any local reaction.	The reaction is reported as "yes" with a diameter of >2.0 cm for redness/swelling or "yes" for pain any day from Day 1 through Day 7.	For all 3 local reactions, participant reports "no" (or "yes" with a diameter ≤2.0 cm for redness/swelling) on all 7 days (Day 1 through Day 7) or as a combination of "no" (or "yes" with a diameter ≤2.0 cm for redness/swelling) and missing on all 7 days. (Day 1 through Day 7).	Participant does not report any data for all 3 local reactions on all 7 days (Day 1 through Day 7).

a. The variables will be derived for any of the local reactions (redness, swelling, and pain at the injection site) and for any of the severe local reactions within the interval from Day 1 through Day 7 after vaccination.

Severity and Maximum Severity

Redness and swelling will be measured and recorded in measuring device units (range: 1 to 21) and then categorized during analysis as absent, mild, moderate, severe, or potentially life-threatening based on the grading scale in Table 5. Measuring device units can be converted to centimeters according to the following formula: 1 measuring device unit = 0.5 cm. Pain at the injection site will be assessed by the participant as absent, mild, moderate, or severe according to the grading scale in Table 5.

Mild Moderate Severe Potentially (Grade 1) Life-Threatening (Grade 2) (Grade 3) (Grade 4) Pain at the Does not interfere Prevents daily Emergency room Interferes with injection site with activity. activity. activity. visit or hospitalization for severe pain. Redness >2.0 cm to 5.0 cm >5.0 cm to 10.0 cm >10 cm Necrosis or (11 to 20 measuring exfoliative

device units).

device units).

>5.0 cm to 10.0 cm

(11 to 20 measuring

(≥21 measuring

(≥21 measuring

device units).

device units).

>10 cm

dermatitis.

Necrosis.

Table 5. Local Reaction Grading Scale

(5 to 10 measuring

>2.0 cm to 5.0 cm

(5 to 10 measuring

device units).

device units).

Swelling

For each local reaction, the maximum severity grade will be derived for the e-diary collection period (Day 1 through Day 7, where Day 1 is the day of each vaccination) as follows:

maximum severity grade = highest grade (maximum severity) within 7 days after vaccination (Day 1 through Day 7) among severity grades where the answers are neither "no" nor missing for at least 1 day during the interval from Day 1 through Day 7.

Duration of Each Local Reaction (First to Last Day Reported)

For participants experiencing any local reactions (or those with a derived reaction as described in Table 4), the maximum duration (resolution date of reaction - start date of reaction + 1) will be derived.

Resolution of the reaction is the last day on which the reaction is recorded in the e-diary or the date the reaction ends if it is unresolved during the participant e-diary recording period (end date collected on the CRF), unless chronicity is established. If there is no known end date, the duration will be considered unknown and set to "missing." Participants with no reported reactions have no duration.

Onset Day of Each Local Reaction

The onset day of each local reaction will be derived. Onset day is defined as the first day of reporting any severity.

For the onset day of each local reaction, if participants report a change in severity of the local reaction, only the first day of reporting that specific local reaction will be counted.

